### **3. CLINICAL HYPOTHESIS**

Severe visual distortions for the TECNIS Toric IOL Models ZCT450, ZCT525 and ZCT600 will be reported in less than 10 percent of the study population.

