## **11.6 POSTOPERATIVE PROCEDURES**

Postoperatively, subjects will be examined according to the schedule in Section 11.2, Visit Schedule. All subjects will be examined at the 1- and 6-month study visits. If a subject requires a lens repositioning procedure due to IOL misalignment or if a subject reports a severe visual distortion at 6 months, the subject will also undergo a final visit at 1 year.

At the 1-month visit, a spectacle and/or contact lens prescription will be offered to each subject. Postoperative procedures will include uncorrected and best corrected visual acuities, manifest refraction, intraocular pressure and biomicroscopic slit-lamp examination. In addition, if the subject has a spontaneous report of any of the 5 visual distortion items of interest or of blurred or hazy vision, the questionnaire will be administered and keratometry and toric IOL axis measurements will be performed.

Primary 6-month postoperative data collection consists of administration of a subject questionnaire for determination of visual distortion reports, manifest refraction, distance visual acuities, intraocular pressure, keratometry, and a biomicroscopic slit-lamp exam for determination of toric IOL axis position and for any adverse events.

If outside of a scheduled study visit, a subject has a spontaneous report of; 1) any of the 5 visual distortion items of interest or 2) blurred or hazy vision at one month postoperatively or later, the PRVDQ questionnaire will be administered and keratometry and toric IOL axis measurements will be performed. Exam details will be documented on an unscheduled visit form.

If a subject reports a severe visual distortion or has experienced a serious or device-related adverse event at any unscheduled study visit, uncorrected distance visual acuity, best corrected distance visual acuity, manifest refraction, keratometry, intraocular pressure and biomicroscopic slit-lam examinations will be performed.

Subjects should be assessed at each visit for occurrence of and/or change in status of any adverse events, particularly serious and/or device-related adverse events. If a serious or device-related adverse event occurs, details of the event are to be captured on an adverse event CRF and the exam details are to be captured on the appropriate visit CRF (i.e., 1-month, 6-month, 1-year or unscheduled). The event will be followed up as necessary and details captured on adverse event follow-up CRFs until resolution.

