#### SUBJECT FOLLOW-UP

To minimize subjects lost to follow-up, subjects will be provided compensation for their time and participation in the study at the 1- and 6-month postoperative exams.

Additionally, sites will be compensated for completion of the 1- and 6-month exams and will be provided frequent listings of upcoming 1- and 6-month subject examinations as well as follow-up reminder cards to send to the subjects. It is anticipated that at least 90% of subjects will be available for the 6-month study visit (i.e., no more than a 10% lost-to-follow-up rate at 6 months postoperatively). If a subject has a confirmed report of severe visual distortion(s) per the questionnaire, prior to the 6-month exam, every effort is to be made to ensure that subject returns for the 6-month exam. The investigative site shall make a minimum of at least three attempts (phone calls/emails and/or letters) to locate missing subjects.

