### **20.3 PRIMARY ENDPOINT**

The primary endpoint for this study is the rate of severe visual distortions (under overall circumstances) as measured by the 5 visual distortion items of interest in bilateral subjects at 6 months. The frequency, proportion and a two-sided 95% confidence interval will be reported for this endpoint. The frequency and proportion of subjects reporting one or more of these items as severe will be used to determine the rate of severe distortions.

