## 20.5 INTERIM REPORTS

Interim status study reports will be provided to FDA every 6 months for the first 2 years following FDA approval of the lens models (July 31, 2015) and annually thereafter, until completion of the post-approval study according to the guidance document entitled "Procedures for Handling Post-Approval Studies Imposed by PMA Order," dated June 15, 2009.

A primary-analysis, 6-month study report will be provided to FDA approximately 3 months following completion of the last 6-month study visit. Any 1-year data collected to date will be included.

A final study report will be provided to FDA approximately 3 months following completion of the last 1-year study visit. Note that the primary-analysis, 6-month report and the final report may be submitted at the same time depending upon when the last 6-month and 1-year exams are completed.

Interim and final study reports will include general enrollment and accountability items including the number of active sites, the number of subjects enrolled, implanted and discontinued and the number of postoperative examinations completed. Interim reports, will only include descriptive statistics (no hypothesis testing). Additional specifics on interim report items include:

- Summary of study progress milestones/timeline elements
- Stratified subject accountability data
- Explanation for any discontinued or lost to follow-up subjects, including deaths
- Summary of safety and effectiveness data using descriptive statistics of study results as of report period
- Rationale for not meeting study milestones/timeline with a revised study timeline, as applicable
- Revised reporting schedule with rationale for revision, as applicable

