## 2. Analysis Populations and Data Conventions

### 2.1 Analysis Population

The primary analysis population will be all bilaterally implanted subjects having available data at the six month visit. In addition, data for severe visual distortions (based on the 5 defined items) will also be reported for all subjects including bilateral subjects and those with only one eye implanted and the fellow eye having phakic status, a cataract, or another IOL. If a subject does not have overall severe visual distortion data available at the six month visit (or had a repositioning procedure or IOL removal performed) then data for the endpoint will be carried forward from the most recent postoperative visit (for general missing data) or the postoperative visit prior to the IOL repositioning or removal. If a subject had an IOL repositioning/removal procedure and did not have visual distortion data available prior to the procedure, then the subject will be considered to have had severe visual distortions for the primary endpoint. For overall severe visual distortions based on the 5 defined items, an additional analysis population will be evaluated that includes all subjects with last observation carried forward for missing data as described above as well as use of data imputation for subjects with no available questionnaire data at any time point. Imputation for those with no questionnaire data will be performed using multiple imputation techniques as described in Little and Rubin and implemented using the MI and MIANALYZE procedures in SAS® (Version 9.2 or later

version if available). Additional sensitivity analyses will be performed including worst-case analysis where all missing visual distortion data (using the 5 defined items) will be treated as having a severe visual distortion and best-case analysis where missing data is treated as having no severe visual distortion. If more than 10 percent of visual distortion data (using the 5 defined items) are missing then a tipping point analysis will also be evaluated.

Data will typically be reported for all bilateral subjects, however, for some analyses, such as the overall visual distortion endpoint, data will also be reported by IOL group. Subjects who have a lower cylinder IOL in one eye (e.g. ZCT300) and a higher cylinder IOL in the fellow eye (e.g. ZCT450) will be placed in the higher cylinder group for analysis when reporting data by subject.

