## 4. Postoperative Analyses – Key Endpoints

### 4.1 Visual Distortions – Primary Endpoint

The primary endpoint is the rate of severe visual distortions defined as the proportion of subjects who report a severe visual distortion under overall circumstances at 6 months for any of the 5 defined visual distortion items listed in section 1.0. The frequency and proportion of bilateral subjects with severe visual distortions will be reported along with the two-sided 95% confidence interval at the 6 month visit. Thus, the statistical focus is to estimate the rate of severe visual distortions.

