#### **7. Sample Size Calculations**

With 80 subjects and a severe visual distortion rate of 0.025, this study has 86% probability of achieving a half-width of 0.05 for a 95% confidence interval for the rate of severe visual distortions.

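### Does the planned tipping-point analysis fail because the SAP names neither a tipping criterion nor a confidence interval method?

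*SAP*

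**What the plan says.** SAP 2.1 sets out the handling of missing data for the primary endpoint: carry-forward, multiple imputation for subjects with no questionnaire at any time, and worst-case and best-case analyses. It then adds that when more than 10% of the five-item data "are missing then a tipping point analysis will also be evaluated". It gives no further detail.

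On the aim of the analysis, SAP 4.1 ends: "Thus, the statistical focus is to estimate the rate of severe visual distortions". Protocol 20.3 agrees: "The frequency, proportion and a two-sided 95% confidence interval will be reported for this endpoint". Neither names the interval method. SAP section 7 gives the planning basis, 80 subjects and a rate of 0.025, for which "this study has 86% probability of achieving a half-width of 0.05 for a 95% confidence interval".

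The figure of 10% as a benchmark for the rate appears only in the protocol (synopsis and section 3), where severe distortions "will be reported in less than 10 percent of the study population". The SAP does not repeat it.

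On missing data, the subject follow-up part of protocol 11.8 expects "no more than a 10% lost-to-follow-up rate at 6 months postoperatively". Before 6 months the postoperative questionnaire is conditional. At 1 month, for example, protocol 11.6 requires a spontaneous report of one of the "items of interest or of blurred or hazy vision, the questionnaire will be administered".

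**The concern.** A tipping-point analysis asks how many missing subjects must be counted as events before a conclusion changes, so it seems to need a stated conclusion. An estimation-only plan supplies none. If 10% is taken as the benchmark, the documents do not say whether it applies to the observed rate or to a confidence limit, nor by which interval method. They also do not say whether the 10% trigger is counted before or after carry-forward.

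In an open-label, single-arm study the analyst would settle these points with the events and missing counts in view. The same data could then be called fragile or robust. The worst-case analysis does not help: with 9 of 80 missing it gives at least 9/80 = 11.25% even with no observed event. Carry-forward may fill few gaps, because most subjects will have no postoperative questionnaire before 6 months. Protocol 20.5 could add to the doubt, since it excludes testing only for interim reports: "Interim reports, will only include descriptive statistics (no hypothesis testing".

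**Working it through.** **Inputs.** N = 80 and rate 0.025 (SAP section 7); trigger above 10% missing (SAP 2.1), so the smallest triggering count is 9, since 8/80 = 10.0% and 9/80 = 11.25%; benchmark 10% (protocol section 3). Assumptions: 9 missing after any carry-forward, and 2 severe among the 71 observed (0.025 × 80 = 2).

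**The plan's own figure.** Take the probability that (upper − lower)/2 ≤ 0.05 when X is binomial(80, 0.025). With Clopper-Pearson, Wilson, mid-P or continuity-corrected Wald the condition holds for X ≤ 3, and P(X ≤ 3) = 0.8594, which is the stated 86%. With plain Wald or Jeffreys it holds for X ≤ 4, giving 0.9496. So the planning figure does not fit plain Wald or Jeffreys, but it does not single out one method.

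**Tipping on the observed rate.** The rate stops being below 10% at 8 events (8/80 = 10.0%). With 2 observed, that takes 8 − 2 = 6 of the 9.

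**Tipping on an upper 95% limit.** Find the smallest total x for which the upper limit for x/80 reaches 10%, then subtract 2. Clopper-Pearson uses the 0.975 quantile of Beta(x + 1, 80 − x). Wilson uses [p + z²/2n + z√(p(1 − p)/n + z²/4n²)]/(1 + z²/n); at 3/80 this is (0.0375 + 0.0240 + 0.0481)/1.0480 = 0.1045.

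| Method | Last x below 10% | First x at or above 10% | Tips at |
|---|---|---|---|
| Clopper-Pearson | 2 (8.74%) | 3 (10.57%) | 1 of 9 |
| Wilson | 2 (8.66%) | 3 (10.45%) | 1 of 9 |
| Mid-P | 3 (9.86%) | 4 (11.62%) | 2 of 9 |
| Wald, continuity-corrected | 3 (8.54%) | 4 (10.40%) | 2 of 9 |
| Jeffreys | 3 (9.67%) | 4 (11.45%) | 2 of 9 |
| Plain Wald | 4 (9.78%) | 5 (11.55%) | 3 of 9 |

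Most of the gap between 1 and 6 therefore comes from comparing two different quantities. Interval method alone moves the count from 1 to 2 among the four methods that fit the 86%, and to 3 with plain Wald.

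**Other observed counts** (Clopper-Pearson limit against observed rate): 0 events, 3 v 8; 1 event, 2 v 7; 3 events, 0 v 5. With 3 events the Clopper-Pearson upper limit for 3/71 is already 11.9%, so on that reading nothing is left to tip.

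**How often this arises.** P(more than 8 of 80 missing) is 41%, 14% and 2% for assumed average losses of 10%, 7.5% and 5%. The protocol gives 10% as a ceiling, not an average. P(2 or fewer events in 71 at 2.5%) = 0.738. If the two are independent, the joint chance is about 0.407 × 0.738 = 30%, 0.145 × 0.738 = 11% and 0.018 × 0.738 = 1.4%.

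**Can it be run as written?** Yes. Count j = 0, 1, …, 9 of the missing as severe and report (2 + j)/80 with its interval. The rate runs from 2/80 = 2.5% to 11/80 = 13.75%, and under Clopper-Pearson the upper limit runs from 8.7% to 23.3%. The table shows where either reading crosses 10%, so no criterion has to be chosen.

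**The case for a change.** The strongest case for a change is that the sponsor committed to this analysis for a safety endpoint imposed as a condition of approval. Worst case and best case only mark the ends of the range, and the tipping-point analysis is the one meant to describe what lies between. A sentence or two would settle it. The unnamed interval also touches the primary result whether or not the trigger is met: at 2/80 the upper limit is 8.7% with Clopper-Pearson and 6.6% with continuity-corrected Wald, and both methods fit the planning figure.

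Part of this stands. The text is silent on the tracked quantity, the interval method and the timing of the trigger count.

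The rest is weaker. The estimation focus and a tipping-point table do not conflict, as the threshold-free version shows. No section ties 10% to a confidence limit. Protocol section 3 speaks of the share of the population reporting severe distortions, and protocol 6.1 defines the rate as a percentage of subjects, so the observed proportion is the natural reading. The remark in protocol 20.5 about interim reports does not imply testing in the final report and is consistent with SAP 4.1. Multiple imputation also covers subjects with no questionnaire data. The interval method does change a reported limit, but no decision rests on that limit.

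**Conclusion.** No change to the plan is needed. This is missing detail that analysts can fill sensibly, not a rule that gives a wrong result. The spread of 1 to 3 against 6 of 9 is correct arithmetic, but it depends on 80 subjects, 9 missing and 2 observed events, on counting 8/80 as no longer below 10% (it would be 7 of 9 if the rate had to exceed 10%), and on a confidence-limit reading that the documents do not state.

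The point estimate is the same under every choice, and no study decision turns on the tipping count. SAP 3.2 and the SAP table listing already provide the number with 6-month data, the numbers with and without severe distortions, and the interval. From these anyone can derive the tipping count for a chosen threshold. Standard practice covers what remains: a conventional binomial interval, stated in the report, and a table over all possible counts among the missing.

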## **2.2 Data Conventions**

Descriptive statistics will typically include sample size (N), mean, standard deviation (SD), minimum (Min), maximum (Max) as appropriate for continuous variables. For categorical data, the frequency and proportion will be computed.

## **2.3 Randomization**

Subjects will not be randomized in this study.

## **3. Accountability/Demographics**

### **3.1 Enrollment**

The number of enrolled subjects will be tabulated by site and by IOL model implanted for primary and fellow eyes.

### **3.2 Accountability**

The frequency and proportion of subjects with six month data will be provided. For those subjects that did not have data available at the six month visit the reasons for the missing visit will be summarized.

### **3.3 Demographics/Preoperative/Operative Parameters**

Subject demographic data including age, sex, race, ethnicity and eye color will be presented. Age will be classified by less than 60, 60 to 69, 70 to 79, and equal to or older than 80 years old. In addition, mean age will be summarized with descriptive statistics. The frequency distributions of sex, race, ethnicity and iris color will also be tabulated.

The frequency and proportion of operative complications and additional operative procedures will be reported for primary and fellow eyes.

## 4. Postoperative Analyses – Key Endpoints

### 4.1 Visual Distortions – Primary Endpoint

The primary endpoint is the rate of severe visual distortions defined as the proportion of subjects who report a severe visual distortion under overall circumstances at 6 months for any of the 5 defined visual distortion items listed in section 1.0. The frequency and proportion of bilateral subjects with severe visual distortions will be reported along with the two-sided 95% confidence interval at the 6 month visit. Thus, the statistical focus is to estimate the rate of severe visual distortions.

### 4.2 Other Visual Distortion Endpoints Related to Severe Visual Distortions

In addition to the above analysis related to the primary endpoint, other analyses will also be performed for severe visual distortion rates (based on the 5 defined items) in the overall circumstance and will include the frequency and proportion with severe visual distortions. Severe visual distortion data for the overall circumstance will be reported by the IOL group for bilateral subjects. The severe visual distortion rate will also be reported for all subjects enrolled in the study including bilateral subjects and those implanted in one eye (with a cataract, phakic condition or having another IOL (i.e. not a ZCT300-ZCT600 IOL) in the fellow eye). A trend analysis will be performed by plotting the severe visual distortion rate by increasing toric IOL cylinder power. To examine within subject changes for visual distortions (based on the 5 defined items in the overall circumstance) for subjects with data at both the 1 month and 6 month visits, the frequency and proportion will be reported for the following categories: those with severe distortions at both visits, those with severe distortions only at 1 month, those with severe distortions only at 6 months and those with no severe distortions at 1 month or 6 months. In addition, for subjects with severe visual distortions (based on the 5 defined items) at any time point, data will be provided indicating when the severe visual distortions were reported and the status at 6 months. Results for severe visual distortions will also be reported by investigational site. Any unusual patterns due to site will be noted (i.e. all severe visual distortions at 1 or 2 sites) and further analyses performed to address any site issues. Details on age, sex, race and cylinder will be reported for subjects experiencing severe visual distortions.

To evaluate if IOL axis misalignment changes are associated with severe visual distortions, descriptive statistics for IOL axis misalignment will be reported for subjects with and without severe visual distortions. In this study, axis misalignment is defined as the difference between the Toric IOL axis marker location from the slit lamp evaluation and the steep meridian from the postoperative keratometry measurement. This measurement is intended to evaluate toric IOL misalignment as a possible reason for severe visual distortions experienced by a subject at a specific postoperative timepoint. This axis misalignment measurement is not a measure of toric IOL rotational stability, but a measure of toric IOL alignment relative to post-surgical keratometry steep meridian [as it is known that cataract surgery can induce changes in the cornea].

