## 11. STUDY PLAN

### 11.1 OVERVIEW

This study will be conducted in accordance with U.S. Code of Federal Regulations, the Declaration of Helsinki, ISO 14155 and all other applicable laws and regulations. The study will not begin until regulatory and IRB approvals have been obtained

This study is a prospective, multicenter, bilateral, non-randomized, open-label, clinical study conducted at up to 20 US sites. Subjects will be bilaterally implanted with high cylinder TECNIS Toric IOLs, Models ZCT300-ZCT600 in both eyes with at least one eye implanted with a Model ZCT450, ZCT525 or ZCT600. The eye with the highest toric power lens will determine the lens group. Second-eye surgeries are to be performed within approximately 1 month (no more than 60 days) of the first-eye surgery, as second-eye cataract surgeries are typically performed within 2 months of the first-eye surgery. Subjects will be examined postoperatively at 1 and 6 months following the second-eye surgery. If a subject requires a lens repositioning procedure due to IOL misalignment or if a subject reports a severe visual distortion at 6 months, the subject will undergo a final visit at 1 year. Additional visit schedule details are provided in Section 11.2 Visit Schedule.

At the 1-month visit, a spectacle and/or contact lens prescription will be offered to each subject. Postoperative procedures will include uncorrected and best corrected visual acuities, manifest refraction, intraocular pressure and biomicroscopic slit-lamp examination. In addition, if the subject has a spontaneous report of any of the 5 visual distortion items of interest or of blurred or hazy vision, the questionnaire will be administered and keratometry and toric IOL axis measurements will be performed.

At the 6-month visit, the postoperative procedures will include a subject questionnaire for determination of visual distortions, keratometry, uncorrected and best corrected visual acuities, manifest refraction, intraocular pressure and a biomicroscopic slit-lamp examination for determination of toric IOL axis position and for any adverse events.

If outside of a scheduled study visit, a subject has a spontaneous report of; 1) any of the 5 visual distortion items of interest or 2) blurred or hazy vision at one month postoperatively or later, the PRVDQ questionnaire will be administered and keratometry and toric IOL axis measurements will be performed. Exam details will be documented on an unscheduled visit form.

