See Section 12.0, Adverse Events, and **Appendix D** Adverse Event Reporting Instructions, for further information.

If a serious or device-related adverse event occurs at or prior to the 6-month visit, details of the event will be collected at the time of the event using an adverse event form. If the adverse event results in an IOL repositioning procedure due to misalignment, the questionnaire should be administered prior to the procedure to collect information regarding visual distortions. Keratometry and toric IOL axis measurements will be performed prior to the repositioning procedure to collect data regarding the IOL misalignment.

If correction is required during the study postoperatively, spectacles or contact lenses will be prescribed; however, no additional refractive procedures (LRI, AK, etc.) are allowed until after completion of the 6-month study visit. If a subject is required to return for a 1-year exam (due to a severe visual distortion at 6 months or an IOL repositioning procedure during the study), a refractive enhancement (LRI, AK, etc.) may be performed prior to the 1-year exam but must be reported on the 1-year case report form; this enhancement will not be considered a secondary surgical intervention at this time.

The postoperative case report form will include the following information (Appendix A):

- Confirmation of offering of spectacle and/or contact lens prescription: 1-month visit only
- Questionnaire: (Following completion of the questionnaire by the subject, the questionnaire is to be reviewed by the site personnel for reports of severe visual distortions), 6-month and 1-year visits and also at 1-month or unscheduled visits only

if there is a spontaneous report of visual distortion or prior to an IOL repositioning procedure at that visit.

- Keratometry: 6-month and 1-year visits; also at 1-month and unscheduled visits if there is a spontaneous report of visual distortion or prior to an IOL repositioning procedure at that visit.
- Monocular uncorrected distance visual acuity, Snellen: all scheduled postoperative visits and unscheduled visits if a severe visual distortion or a serious or device-related adverse event is reported at that visit.
- Binocular uncorrected distance visual acuity, Snellen: 1- month, 6-month and 1-year visits; also at unscheduled visits if a severe visual distortion or a serious or device-related adverse event is reported at that visit.

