### 20.2 ANALYSIS POPULATION

For the primary endpoint and most visual distortion endpoints, the primary analysis population will be all bilaterally implanted subjects having available data at the 6-month visit. Data will also be reported for all subjects including bilateral subjects and those with only one eye implanted (having a phakic lens, a cataract or other IOL in the fellow eye). Data will also be reported by IOL group. If a subject does not have overall severe visual distortion data available at the 6-month visit (or had a repositioning procedure or IOL removal performed) then data for this endpoint will be carried forward from the most recent visit (for general missing data) or the visit with data taken prior to the IOL

repositioning or removal. If a subject had an IOL repositioning/removal and no questionnaire data prior to the procedure, then the subject will be considered to have had a severe visual distortion for this endpoint. An additional analysis will be performed for the primary endpoint using multiple imputation techniques for those with no questionnaire data available. Sensitivity analyses such as worst-case and best-case will also be performed.

Refraction, visual acuity, medical/lens findings, axis evaluation and adverse events will be reported for primary eyes (those having the higher cylinder IOL or the first eye implanted if the same IOL is implanted in both eyes) and fellow eyes. Data will be reported separately for ZCT450-ZCT600 eyes and ZCT 300-ZCT400 eyes.

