## APPENDIX A SUMMARY OF PROCEDURES REQUIRED AT EACH VISIT

Examination	Preoperative Both eyes	Op 1 1 st eye	Op 2 2 nd eye	Unscheduled Visit	1 Month Both eyes	6 Months Both eyes	1 Year a Both eyes
X = To be performed							
A = To be performed if a visual distortion is spontaneously reported prior to 6 month exam or prior to a required IOL repositioning (adverse event)							
B =To be performed if a subject reports a severe visual distortion or experiences a serious or device-related adverse event at this visit.							
O = Only if medically indicated							
Ocular history, inclusion/exclusion criteria	X						
Informed consent	X						
Potential visual acuity	X						
Targeted refraction/Targeted cylinder/IOL power calculations b /axial length	X						
Lens power/serial number/operative procedures		X	X				
UCDVA-photopic, monocular (Snellen)	X			B	X	X	X
UCDVA-photopic, binocular (Snellen)				B	X	X	X
Manifest refraction (Snellen)	X			B	X	X	X
BCDVA-photopic, monocular (Snellen)	X			B	X	X	X
BCDVA-photopic, binocular (Snellen)				B	X	X	X
Offer spectacle and/or contact lens prescription					X		
Keratometry	X			A/B	A	X	X
Intraocular pressure	X			B	X	X	X
Biomicroscopic slit-lamp exam c	X			B	X	X	X
Toric IOL axis measurement at dilated slit-lamp exam				A	A	X	X
Dilated fundus exam	X			O	O	O	O
Adverse events		X	X	X	X	X	X
Ocular medications	X			X	X	X	X
Subject questionnaire	X			A	A	X	X

a Examination at 1 year is to be conducted ONLY if a subject reported a severe visual distortion at 6 months or if the subject experienced an IOL repositioning procedure (due to IOL misalignment) during the study.

b Includes documentation of toric IOL calculations showing chosen ZCT for each eye and targeted cylinder outcome

c Includes determination of medical and lens findings/complications, including lens rotation

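### The 1-month versus 6-month change table in SAP 4.2 covers only subjects whose 1-month questionnaire was triggered, so its proportions are not study-population rates

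*SAP*

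**What the plan says.** SAP 4.2 plans a four-category table: severe at both visits, only at 1 month, only at 6 months, or at neither. It is based on the five PRVDQ items in the overall circumstance, and "for subjects with data at both the 1 month and 6 month visits, the frequency and proportion will be reported for the following categories".

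Protocol 11.1 makes the 1-month form conditional: "if the subject has a spontaneous report of any of the 5 visual distortion items of interest or of blurred or hazy vision, the questionnaire" is given. The form schedule in Protocol 11.6 lists it at "6-month and 1-year visits and also at 1-month or unscheduled visits only" where there is a spontaneous distortion report or a repositioning is about to take place. In Protocol Appendix A the questionnaire is an unconditional entry at 6 months. At 1 month it carries a code meaning that it is done "if a visual distortion is spontaneously reported prior to 6 month exam or prior to a required IOL repositioning".

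For subjects severe at any time, SAP 4.2 adds that "data will be provided indicating when the severe visual distortions were reported and the status at 6 months".

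On missing 6-month data, SAP 2.1 says "data for the endpoint will be carried forward from the most recent postoperative visit (for general missing data", whereas Protocol 20.2 says "data for this endpoint will be carried forward from the most recent visit (for general missing data". SAP 2.1 also plans "data imputation for subjects with no available questionnaire data at any time point". Protocol 11.3 and Appendix A require a questionnaire from every subject before surgery.

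**The concern.** A table of persistence, resolution and late onset needs both measurements on a group that represents the study population. Here the 1-month measurement exists mainly because the subject complained. Requiring data at both visits selects on something closely related to the outcome.

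Two categories lose their apparent meaning. The clearest late-onset case, with no complaint at 1 month and a severe distortion at 6 months, cannot enter the category for severe only at 6 months. Most subjects who are well throughout cannot enter the category for no severe distortion at either visit. A reader of the study report could take the remaining proportions as rates for the implanted population, in a study whose purpose is to estimate severe distortion.

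A smaller issue concerns the primary endpoint. General carry-forward draws on the same triggered forms, so it recovers missing subjects selectively. The two documents also differ on whether a preoperative form may be carried forward.

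**Working it through.** **The plan's own figure.** The only calculation stated is the precision statement: 80 subjects, rate 0.025, 86% probability of a 95% interval half-width of at most 0.05. With X ~ Bin(80, 0.025), the Clopper–Pearson half-width is 0.0490 at X = 3 and 0.0547 at X = 4. The probability is P(X ≤ 3) = 0.8594, so the 86% reproduces. It concerns the 6-month rate and does not bear on the change table.

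**Who is in the table.** The variable is the PRVDQ result, and a subject with no trigger has no 1-month PRVDQ. The carry-forward, imputation and worst-/best-case rules in SAP 2.1 concern missing endpoint data. None says that an untriggered subject counts as not severe at 1 month. Appendix I of the SAP does not list the change table, so no footnote or denominator rule is given there. The selection follows from the text alone.

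**Size, under assumed inputs.** The documents give no complaint rate. Inputs:

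- 1-month severe rate 0.025 (assumed; borrowed from the 6-month planning rate)
- s = share of severe subjects who complain spontaneously, 0.6 or 0.9 (assumed)
- q = share of other subjects who complain, including of blurred or hazy vision, 0.05, 0.10 or 0.20 (assumed)
- 72 subjects with 6-month data: 80 × 0.90, from the retention expected in Protocol 11.8

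Triggered share f = 0.025·s + 0.975·q. Table size = 72·f. Apparent 1-month severe share = 0.025·s / f.

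| s | q | f | Table size | Apparent severe share |
|---|---|---|---|---|
| 0.6 | 0.05 | 0.0638 | 4.6 | 23.5% |
| 0.9 | 0.05 | 0.0713 | 5.1 | 31.6% |
| 0.6 | 0.10 | 0.1125 | 8.1 | 13.3% |
| 0.9 | 0.10 | 0.1200 | 8.6 | 18.8% |
| 0.6 | 0.20 | 0.2100 | 15.1 | 7.1% |
| 0.9 | 0.20 | 0.2175 | 15.7 | 10.3% |

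Between 56 and 67 of the 72 subjects fall outside the table (72 − 15.7 to 72 − 4.6). The apparent severe share is 7% to 32% against an assumed true 2.5%.

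One severe subject is 1/5 = 20% (exact 95% CI 0.5–72%) or 1/16 = 6% (0.2–30%) of the table, against 1/72 = 1.4% (0.04–7.5%) of the cohort.

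**A wider trigger range.** Suppose 5% to 50% of the 72 are triggered and two are severe at 6 months. The denominator runs from 4 to 36. If both severe subjects were triggered, the table shows 2/4 = 50% down to 2/36 = 5.6% severe at 6 months, against 2/72 = 2.8%. If neither was triggered, it shows 0%.

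**Carry-forward.** Assume 8 of 80 subjects lack 6-month data, independently of any severe report, and count 1-month forms only.

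- Missing subjects with a postoperative form: 8·f = 0.51 to 1.74
- Expected severe reports among them: 8 × 0.025 × s = 0.12 to 0.18
- Primary rate: (72 × 0.025 + 0.2·s) / (72 + 8·f) = (1.8 + 0.2·s) / (72 + 8·f) = 2.6% to 2.7%, against 2.5%
- Missing subjects with no postoperative form: 8 − 1.74 to 8 − 0.51 = 6.3 to 7.5

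Under the protocol's carry-forward wording those 6.3 to 7.5 subjects would contribute a preoperative answer. Under the SAP's wording they would not. The imputation rule reaches them only if its reference to time points means postoperative ones, because every subject should have a preoperative form.

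**The case against.** The table is secondary and descriptive. It has no test, interval or decision rule, and the primary endpoint uses the routine 6-month form. The SAP states its denominator and reports counts, so a small table would be visible. Late-onset cases still appear in the timing data of SAP 4.2 and in the Appendix I listing of severe subjects. All of this stands and limits the consequence. It does not supply a full-cohort denominator or tell the reader that entry to the table depended on a complaint.

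One could also read the SAP's reference to data at both visits as including an attended 1-month visit with no complaint, counted as not severe. No rule says so, and tying the table to the five questionnaire items points the other way.

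The complaint rates are assumptions, and the 7–32% range moves with them. That is true, but the selection does not depend on their values. The carry-forward illustration omits forms from unscheduled visits, which would raise the number of subjects recovered. Protocol 11.8 asks for every effort to bring back subjects with a confirmed severe report, which would lower the effect.

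Finally, the SAP's word postoperative can be taken as refining the protocol's shorter phrase, and a reading that leaves imputation with no eligible subjects is implausible. Both are probably the intent. The texts still differ on a primary-endpoint rule, and a short wording change would settle each.

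**Conclusion.** The point holds. As written, the SAP 4.2 change table describes subjects whose 1-month questionnaire was triggered by a complaint or an impending repositioning. Its proportions do not estimate persistence, resolution or late onset in the bilateral population. This rests on the text and needs no assumed figure.

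The size rests on the assumed complaint rates, a 2.5% 1-month severe rate and 90% retention: about 5 to 16 of 72 subjects in the table, and an apparent severe share of 7% to 32%.

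For the primary endpoint the effect is small and upward, which is conservative for a safety rate. The planned imputation and worst-/best-case analyses largely cover it, provided imputation can reach subjects with no postoperative form. The change should be made, but the primary analysis does not depend on it.

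**What to change.** 1. Base the SAP 4.2 table on all bilateral subjects with 6-month data. Cross-classify 6-month status (severe, not severe) by 1-month status (severe, not severe, no PRVDQ triggered).
2. State that 1-month proportions among triggered subjects are not population rates, and add the table to Appendix I.
3. Keep carry-forward, but report how many subjects and events were carried. Show the rate from observed 6-month data beside the primary result.
4. Reconcile the carry-forward wording of Protocol 20.2 with SAP 2.1, and say whether the time points in the imputation rule are postoperative only.
5. Reconcile the 1-month trigger across the protocol. The narrative in 11.1 and 11.6 includes blurred or hazy vision, as does 11.7 for unscheduled visits. The form schedule in 11.6 and Appendix A do not. The trigger decides who has 1-month data.

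The cost is wording in both documents and slightly more table work. The data are already collected, and no visit or form is added.
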